9.6.2 Primary Objective: Secondary Estimand Analysis

9.6.2.1 Secondary Estimand

This analysis refers to the secondary estimand of the primary objective defined in section 3.1. This estimand is implementing the “treatment policy strategy” and reflects the intention-to-treat (ITT) principle. It will evaluate the effect of switching to THS as compared to continuing to smoke CIG in the FAS rather than in the PPS. It is defined by the following components:

1. **Product Use Under Evaluation:** This corresponds to the study arm (CIG, THS Blade device, THS Induction Mono device or THS Induction Mid device) randomly allocated to subjects and is independent of whether subjects were adherent or not (FAS).
2. **Target Population:** This is the population of adult smokers who satisfy all eligibility criteria (see section 4.5.1).

1. **Variables of Interest:** 3-HPMA, 2CyEMA, MHBMA, total NNAL (all expressed as concentration adjusted for creatinine in 24-hour urine), and COHb (expressed as % of saturation of hemoglobin).

Confidentiality Statement

Data and information contained in this document are considered to constitute trade secrets and confidential commercial information, and the legal protections provided to such trade secrets and confidential information are hereby claimed under the provisions of applicable law. No part of this document may be publicly disclosed without the written consent of Philip Morris Products S.A

2. **Intercurrent Events (ICEs)**: All ICEs will be treated as ‘treatment policy strategy’. This means that the values of the variable of interest is used regardless of whether the ICEs occur.
3. **Population-Level Summary Statistic**: Geometric mean ratios between each THS arm (THS Blade device, THS Induction Mono device or THS Induction Mid device) and CIG of the BoExp under consideration at Day 5.

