**Confidentiality Statement**

Data and information contained in this document are considered to constitute trade secrets and confidential commercial information, and the legal protections provided to such trade secrets and confidential information are hereby claimed under the provisions of applicable law. No part of this document may be publicly disclosed without the written consent of Philip Morris Products S.A.

Subjects will be informed of their randomized study arm by the study site staff on Day 1 prior to 06:30 AM.

Exposure in confinement (Day 1, 06:30 AM until Day 5, 11:00 PM):

The exposure period will consist of 5 days of *ad libitum* use of the assigned investigational product between 06:30 AM and 11:00 PM in the THS and CIG arms. Use of any TNP other than the assigned investigational product (or CIG smoking in the CIG arm) will not be allowed and may, at the discretion of the Investigator, result in discontinuation of the subject from the study.

Daily 24-hour urine will be collected from Day 1 to Day 5. On Day 1, product use must not start before the end of 24-hour urine collection of Day -1. The 24-hour urine collection period for Day 5 will end in the morning of Day 6 prior to discharge.

During the confinement period, site staff will distribute assigned products to the subjects and record all products distributed in the source documentation.

Discharge period (Day 5, 11:01 PM until Day 6, time of Discharge):

Discharge procedures, including laboratory parameters, will be conducted to discharge the subject from the clinic after 7 days in a confined setting. Use of CIG will be allowed on Day 6 once all study procedures are completed.

Safety follow-up (Day 6, time of Discharge, to Day 9):

After Discharge on Day 6, or after Early termination, subjects will enter a 3-day Safety follow-up period during which AEs/SAEs will be collected and follow-up of any ongoing AEs/SAEs will be conducted by investigational site. The end of the study is defined as the completion of the 3-day Safety follow-up period either after the Discharge on Day 6, or after Early termination.

During the study, subjects in the CIG arm and the THS arms who want to quit smoking will receive appropriate medical advice. This will not affect subject's financial compensation, and the subject will remain in the study.

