### Confidentiality Statement

Data and information contained in this document are considered to constitute trade secrets and confidential commercial information, and the legal protections provided to such trade secrets and confidential information are hereby claimed under the provisions of applicable law. No part of this document may be publicly disclosed without the written consent of Philip Morris Products S.A.

Subjects will be informed that they are free to withdraw from the study at any time. Subjects should be questioned for the reason of withdrawal from the study, although they are not obliged to disclose it.

If the subject withdraws from the study, this information will be fully documented by the PI or designee including:

- The early termination procedures for safety assessments will be performed as defined in section 9.6, unless the subject refuses to perform the assessments.
- The samples collected up to the time of withdrawal that have been analyzed and data collected up to the time of withdrawal will be used in the analysis and report. If the subject refuses that non-analyzed samples and data will be used, he/she needs to document his/her disagreement in writing.

Subjects must be discontinued from the study for any of the following reasons:

- Withdrawal of informed consent
- Non-adherence to allocated product
- Subject becomes an employee of the investigational site or any other parties involved in the study or their first-degree relatives (parent, sibling, and child)
- Any AE or condition (including clinically significant changes in a laboratory parameter) which at the discretion of the Investigator no longer justifies the subject's participation in this study
- Positive pregnancy test
- Discontinuation considered to be in the best interest of the subject or the other subjects, as judged by the Investigator
- Subject unwilling to use the product during the entire study duration after having done the product test
- An alternate subject that has completed the 28-day Screening period and has not been randomized
- The Sponsor terminates the study, or the study terminates at a particular site. If the Sponsor decides to prematurely terminate the study, the subjects will be promptly informed. The Investigator or designee should report the fact and the reason in writing to the IEC

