**Table 11 Time Schedule – Early Termination Visit**

| Procedures   | Additional Information   |
|--|--|
| Collection of blood sample   | After $\geq 6$ hours of fasting, if possible
- Safety panel |
| Collection of spot urine   | - Safety panel
- Pregnancy test (WOCBP only)                |
| Vital signs  |  |
| ECG  |  |
| Spirometry   |  |
| Information on smoking risks; advice on smoking cessation; and briefing on THS |  |
| Concomitant medication   |  |
| Concomitant diseases   |  |
| AE/SAE recording   |  |
| THS product events and complaints  | THS arms only  |
| Discharge  |  |

Abbreviations:

AE = Adverse event; ECG = Electrocardiogram; SAE = Serious adverse event; THS = tobacco heating system; WOCBP = women of child-bearing potential

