#### 12.5.2.3 Missing Data Strategy

In this analysis, some missing data might occur because of missing samples, laboratory measurements errors, etc. The main analysis model (see section 12.5.2.4) assumes that subjects with missing data would have outcome data like those in similar subjects in the same group (MAR assumption). This assumption is aligned with the definition of the secondary estimand.

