Daily 24-hour urine will be collected from Day 1 to Day 5. On Day 1, product use must not start before the end of 24-hour urine collection of Day -1. The 24-hour urine collection period for Day 5 will end in the morning of Day 6 prior to discharge.

During the confinement period, site staff will distribute assigned products to the subjects and record all products distributed in the source documentation.

Discharge period (Day 5, 11:01 PM until Day 6, time of Discharge):

Discharge procedures, including laboratory parameters, will be conducted to discharge the subject from the clinic after 7 days in a confined setting. Use of CIG will be allowed on Day 6 once all study procedures are completed.

Safety follow-up (Day 6, time of Discharge, to Day 9):

After Discharge on Day 6, or after Early termination, subjects will enter a 3-day Safety follow-up period during which AEs/SAEs will be collected and follow-up of any ongoing AEs/SAEs will be conducted by investigational site. The end of the study is defined as the completion of the 3-day Safety follow-up period either after the Discharge on Day 6, or after Early termination.

During the study, subjects in the CIG arm and the THS arms who want to quit smoking will receive appropriate medical advice. This will not affect subject's financial compensation, and the subject will remain in the study.

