4.5.3 Discontinuation of Subjects from the Study

Discontinued subjects (i.e., enrolled subjects that do not complete the study) will include both subjects who withdraw from the study (subject's decision) or subjects who are discontinued from the study by the decision of the Investigator.

Subjects will be informed that they are free to withdraw from the study at any time. Subjects should be questioned for the reason of withdrawal from the study, although they are not obliged to disclose it.

If the subject withdraws from the study, this information will be fully documented by the PI or designee including:

- The early termination procedures for safety assessments will be performed as defined in section 13.1, unless the subject refuses to perform the assessments.
- The samples collected up to the time of withdrawal that have been analyzed and data collected up to the time of withdrawal will be used in the analysis and report. If the subject refuses that non-analyzed samples and data will be used, he/she needs to document his/her disagreement in writing.

Subjects must be discontinued from the study for any of the following reasons:

- Withdrawal of informed consent
- Non-adherence to allocated product
- Subject becomes an employee of the investigational site or any other parties involved in the study or their first-degree relatives (parent, sibling, and child)
- Any AE or condition (including clinically significant changes in a laboratory parameter) which at the discretion of the Investigator no longer justifies the subject's participation in this study
- Positive pregnancy test
- Discontinuation considered to be in the best interest of the subject or the other subjects, as judged by the Investigator
- Subject unwilling to use the product during the entire study duration after having done the product test
- An alternate subject that has completed the 28-day Screening period and has not been randomized
- The Sponsor terminates the study, or the study terminates at a particular site. If the Sponsor decides to prematurely terminate the study, the subjects will be promptly

Confidentiality Statement

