8.5.1 Major Protocol Deviations

Protocol deviations are defined as any deviation from the procedures defined in the protocol. Major deviations will include, but are not limited to, the categories outlined in [Table 9](#).

Table 9 Major Protocol Deviations with Impact on Evaluability

Category	Description
Any violation of inclusion/exclusion criteria	Considered a major deviation. The blinded data review team will decide on whether it impacts evaluability.
Mis-randomization (wrong information provided to randomization system)	Considered a major deviation with impact on evaluability. Mis-randomized subjects will be classified according to their actual exposure arm for safety analysis.
Use of any nicotine or tobacco-containing product other than the assigned product during the exposure period	Considered a major deviation. The blinded data review team will decide on whether it impacts evaluability.
Assessments related to the primary and key secondary objectives performed outside the time tolerance (see Table 10)	Considered a major deviation. The blinded data review team will decide on whether it impacts evaluability.

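### For subjects who discontinue during exposure, the FAS analysis does not deliver the treatment-policy estimand it is labelled with

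*SAP*

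**What the plan says.** **Estimand.** SAP 9.6.2.1 and Protocol 12.5.2 apply a treatment-policy strategy to every intercurrent event in the FAS and invoke the ITT principle. The SAP explains: "This means that the values of the variable of interest is used regardless of whether the ICEs occur". The events themselves are listed under the primary estimand (SAP 9.6.1.1). They include non-adherence and study discontinuation or death.

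**What follows non-adherence.** The documents give two rules.
- Protocol 5.2 and SAP 4.5.3 give a mandatory list, introduced by "Subjects must be discontinued from the study for any of the following reasons". One item is "Non-adherence to allocated product".
- Protocol 4.1 and SAP 4.1 say that use of another tobacco or nicotine product "will not be allowed and may, at the discretion of the Investigator, result in discontinuation of the subject from the study".

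**Sampling.** Protocol Table 11 lists a safety panel, spot urine, vital signs, ECG, spirometry and event recording at early termination. It lists neither COHb nor 24-hour urine. Both schedules of events show those samples on Day -1 to Day 5 only.

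**Missing data.** Protocol 12.5.2.3 says the model "assumes that subjects with missing data would have outcome data like those in similar subjects in the same group (MAR assumption", and states that this fits the secondary estimand. SAP 9.6.2 has no text on missing data. SAP 9.6.2.2 reuses the primary mixed model on all available FAS data and treats the result as exploratory.

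**The concern.** A treatment-policy estimand needs outcome values after the intercurrent event, or a missing-data assumption that describes what subjects do after it. Discontinuation is itself a listed event, and no exposure biomarker is taken after it, whatever its cause.

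MAR within arm says that a lost THS subject would have looked like comparable THS subjects who are still being sampled. Protocol 6.2.5 instead leaves subjects free to return to their usual products after early termination, and inclusion criterion 4 puts that habit at an average of 10 or more cigarettes a day.

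The primary analysis excludes non-adherent subjects, and the trial is open-label. The FAS analysis is therefore its planned ITT counterpart. At stake is whether a result that leans towards the adherent effect gets reported as ITT support.

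**Working it through.** **1. Where values exist.** Protocol 7.3.10 budgets 30 mL of blood for COHb at 5 mL per sample: 30 / 5 = 6 samples. That matches Day -1 and Days 1 to 5 and leaves none for early termination. The 24-hour urine schedule also has six collections. A subject discontinued before the Day 5 samples has no Day 5 value.

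**2. The plan's own figure.** The plan states no figure for the secondary estimand. Its power claim for the primary objective (above 99% per biomarker) reproduces. The weakest of the 20 rows in SAP Table 7 is 3-HPMA in NCT01970982 (GMR 52.86%, GCV 39.57%):
- SD(log) = √ln(1 + 0.3957²) = 0.3814
- SE at 20 per arm = 0.3814 × √(2/20) = 0.1206
- Noncentrality = 0.6375 / 0.1206 = 5.29 on 38 df; power 99.93% (one-sided 2.5%)
- At 17 per arm (15% missing): 99.71%

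**3. Treatment-policy ratio.** Assume that the planning GMR describes adherent subjects, and that a fraction f of a THS arm is at CIG level on Day 5 and unsampled. Then the treatment-policy ratio is GMR^(1−f). The documents give no non-adherence rate, so f is shown over a range. At 20 per arm, 5% is one subject and 15% is three.

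| Row (SAP Table 7) | Planning GMR | f = 5% | f = 10% | f = 15% |
|---|---|---|---|---|
| 3-HPMA, NCT01970982 (JP) | 52.86% | 54.57% | 56.34% | 58.16% |
| MHBMA, NCT01989156 (US) | 12.58% | 13.95% | 15.48% | 17.17% |
| MHBMA, NCT01959932 (EU) | 8.38% | 9.49% | 10.74% | 12.16% |

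If no non-adherent day was sampled, the MAR model still returns about the planning GMR. The treatment-policy ratio then exceeds the MAR estimate by a factor of GMR^(−f). Over the 20 primary rows this is 1.03 to 1.13 at f = 5% and 1.10 to 1.45 at f = 15%.

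**4. If a non-adherent day was sampled first.** The model conditions on observed days and recovers part of the shift. Take two time points with equal variances, within-subject correlation ρ, and a last sampled day that has moved a fraction k of the way (log scale) to CIG level. The MAR estimate tends to GMR^(1−ρfk). For MHBMA (US) at f = 15%, where the treatment-policy value is 17.17%:
- ρ = 0.3, k = 0.5: 0.1258^0.9775 = 13.18% (simulation 13.21%)
- ρ = 0.7, k = 1: 0.1258^0.895 = 15.64% (simulation 15.62%)

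Both ρ and k are assumptions. The bias is smaller here but not removed.

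**5. Power for the treatment-policy contrast.** Mixing adherent and non-adherent subjects adds f(1−f)(ln GMR)² to the THS variance. For 3-HPMA in NCT01970982 at f = 15%:
- THS variance = 0.1455 + 0.1275 × 0.4064 = 0.1973
- SE = √((0.1455 + 0.1973)/20) = 0.1309
- Noncentrality = 0.85 × 0.6375 / 0.1309 = 4.14; power 98.1%

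This is the lowest of the 20 rows, for one biomarker in one arm with 20 values per arm.

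**The case against.** **Is the estimand inestimable?** A reader might infer this from the mandatory discontinuation list. The documents do not support it. The discretionary wording stands beside the mandatory one, and SAP Table 9 treats use of another product case by case: "Considered a major deviation. The blinded data review team will decide on whether it impacts evaluability". On subjects who want to quit, SAP 4.1 says: "This will not affect subject's financial compensation, and the subject will remain in the study". Such subjects can supply values after the event. This stands, and it confines the point to subjects who discontinue.

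**Must the FAS and per-protocol results agree by construction?** This does not follow either. The FAS keeps mis-randomized subjects, sampled days of non-adherent subjects and values after a positive SARS-CoV-2 test. The per-protocol analysis drops these. Eligibility violations and out-of-window assessments may also separate the two sets.

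**Is 5% to 15% realistic?** Subjects are confined, products are handed out singly, and every used stick and butt is returned. The plan's 15% is a conservative total for missing values of all causes, not a rate of return to smoking. Actual non-adherence may be rarer. The table shows sensitivity and is not a forecast.

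**Does Protocol 12.5.2.3 already cover discontinuation?** Its list of causes is open-ended, so it may. Unlike 12.5.1.3, it does not name intercurrent events. In either case the values would be handled by MAR within arm, which is the difficulty.

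**Does it matter for an exploratory analysis?** It changes no decision. It does change what the reported ratio means.

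**Conclusion.** The point holds for subjects who discontinue during exposure. For their later days the FAS analysis follows a hypothetical strategy, and the statement in Protocol 12.5.2.3 that MAR fits the treatment-policy estimand is not justified. The estimand is partly, not wholly, unobserved.

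Under the assumptions in step 3, the MAR ratio overstates the reduction: the treatment-policy ratio would be 3% to 45% higher in relative terms, depending on biomarker and f. The overstatement is less where non-adherent days were sampled, and shrinks towards nothing if hardly anyone discontinues. The ratios stay far below 1 throughout.

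The formal success decision is not affected, because SAP 9.6.3.1 bases it on the per-protocol set. The planned power is not affected either.

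The protocol read here is version 2.0, while the SAP was aligned to version 3.0. SAP 2.1 gives the purpose of that amendment as the timing of the COHb sample, and the SAP's own schedule still shows exposure biomarkers on the same six days.

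**What to change.** 1. In SAP 9.6.2 and Protocol 12.5.2.3, state that the MAR analysis of the FAS is hypothetical for days after discontinuation. Remove the statement that MAR is aligned with the treatment-policy estimand.
2. Add one FAS sensitivity analysis in which THS values after discontinuation are imputed from the CIG arm (jump to reference). Describe it as a conservative bound, not as the estimator of the estimand: non-adherence may have been a single cigarette or partial use, and full CIG exposure would then overstate it. Report it beside the MAR ratios at Day 5.
3. Reconcile Protocol 5.2 and SAP 4.5.3 (mandatory discontinuation) with Protocol 4.1 and SAP 4.1 (investigator discretion) on what follows non-adherence. The choice between them is for the sponsor and investigators.

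The cost is a wording change in both documents and one extra analysis. No new samples or subjects are needed. The FAS ratios may look slightly less favourable in the added analysis.

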9.6.2.2 Main Analysis

This analysis will be conducted using the same model as the one described in section [9.6.1.2](#), except that it will use the FAS instead of the PPS and all available data will be included in the model.

In section [9.6.1.2](#) the criterion to declare the study successful was provided. For the secondary estimand, the same difference will be computed and interpreted exploratorily using the same type I error level as for the primary confirmatory hypothesis.

9.6.2.3 Supplementary Analysis

The model described in section [9.6.2.3](#) allows contrasting all randomization study arms at Days 1, 2, 3, 4, and 5. The following pairwise comparisons at Days 1, 2, 3, 4, and 5 will be reported, together with their unadjusted p-values and 95%-confidence interval:

1. THS arms jointly (THS Blade device, THS Induction Mono device or THS Induction Mid device) vs. CIG
2. THS Blade device vs. CIG
3. THS Induction Mono device vs. CIG
4. THS Induction Mid device vs. CIG

As in the primary estimand analysis, the contrasts THS Blade device vs. CIG and THS Induction Mono device vs. CIG and THS Induction Mid device vs. CIG will also be estimated one-sided with a type I error level of 2.5% through the additional ‘ls mestimate’ statements provided in section [9.6.1.2](#). These contrasts will be used exploratorily to assess the key secondary objectives 1, 2 and 3 if the procedure of fixed sequence testing allows.

Descriptive statistics as mentioned in section [9.1.3](#) for the variables of interest and associated changes from baseline will be reported by randomization study arm for the FAS and by study day. Descriptive statistics stratified by the factor described in section [9.1.1](#) will also be computed.

Confidentiality Statement

Data and information contained in this document are considered to constitute trade secrets and confidential commercial information, and the legal protections provided to such trade secrets and confidential information are hereby claimed under the provisions of applicable law. No part of this document may be publicly disclosed without the written consent of Philip Morris Products S.A.

9.6.3 Secondary Objective Analyses

[figure not shown]
9.6.3.1 Key Secondary Objectives

The key secondary objectives are to demonstrate the reduction of additional BoExp to selected HPHC given in [Table 2](#) in smokers who switch from CIGs to THS use compared to those who continue to smoke CIG. The statistical analysis for each of these additional BoExp for each THS arm (THS Blade device, THS Induction Mono device or THS Induction Mid device) will be done similarly to those belonging to the primary objective (except the Success Criteria). More specifically, the analyses described as primary estimand (see section [9.6.1.2](#)) can be repeated, replacing the endpoints listed in [Table 1](#) by those of [Table 2](#) and performing the analysis by THS arm sequentially.

The evaluation of the key secondary objectives will be done using a procedure of fixed sequence testing (see [Figure 2](#)). This first key secondary objective related to the THS Blade device will only be tested if the primary objective is demonstrated for all THS arms. This fixed sequence of study hypotheses ensures that the overall study-wise risk of type I error is preserved at the 2.5%.

If both the primary and first key secondary objectives are declared successful, then the 2nd key secondary objective will be tested with type I error level of 2.5%, this time using the contrast THS Induction Mono device vs. CIG and the BoExp listed in [Table 2](#). If this 2nd key secondary objective is also declared successful, then the 3rd key secondary objective can be tested similarly for the THS Induction Mid device arm. If, along the procedure from the primary objective up to the 3rd key secondary objective, any of the objectives are not declared successful, the sequence testing will stop, and further testing will not be permitted.

Figure 2. Representation of the Procedure of Fixed Sequence Testing

Confidentiality Statement

Data and information contained in this document are considered to constitute trade secrets and confidential commercial information, and the legal protections provided to such trade secrets and confidential information are hereby claimed under the provisions of applicable law. No part of this document may be publicly disclosed without the written consent of Philip Morris Products S.A.

Note that, at each level of testing, all BoExp need to lead to a statistically significant test. If the statistical test for one of the BoExp for the given arm (or combination of arm) does not reach statistical significance (at the 2.5% level), then the corresponding level of testing cannot be declared successful, and the fixed sequence testing will stop.

The formal testing procedure of this study will use the primary estimand based on the PPS (see section 8.3). The procedure will be repeated exploratorily using the FAS (see section 8.2).

